10.3 Attribution to agent(s) or procedure

When assessing whether an adverse event (AE) is related to a medical agent(s) medical or procedure, the following attribution categories are utilized:

Definite - The AE *is clearly related* to the agent(s)/procedure.

Probable - The AE *is likely related* to the agent(s)/procedure.

Possible - The AE *may be related* to the agent(s)/procedure.

Unlikely - The AE *is doubtfully related* to the agent(s)/procedure.

Unrelated - The AE *is clearly NOT related* to the agent(s)/procedure.

10.31 AEs Experienced Utilizing Investigational Agents and Commercial Agent(s) on the SAME (Combination) Arm

NOTE: When a commercial agent(s) is (are) used on the same treatment arm as the investigational agent/intervention (also, investigational drug, biologic, cellular product, or other investigational therapy under an IND), the **entire combination (arm) is then considered an investigational intervention for reporting.**

- An AE that occurs on a combination study must be assessed in accordance with the guidelines for **investigational** agents/interventions.
- An AE that occurs prior to administration of the investigational agent/intervention must be assessed as specified in the protocol. In general, only Grade 4 and 5 AEs that are unexpected with at least possible attribution to the commercial agent require an expedited report, unless hospitalization is required. Refer to Section 10.4 for specific AE reporting requirements or exceptions.

An investigational agent/intervention might exacerbate the expected AEs associated with a commercial agent. Therefore, if an expected AE (for the commercial agent)

occurs with a higher degree of severity or specificity, expedited reporting is required.

- An increased incidence of an expected adverse event (AE) is based on the patients treated for this study at their site. A list of known/expected AEs is reported in the package insert or the literature, including AEs resulting from a drug overdose.
- Commercial agent expedited reports must be submitted to the FDA via MedWatch 3500A for Health Professionals (complete all three pages of the form).

Instructions for completing the MedWatch 3500A:

10.32 **EXPECTED Serious Adverse Events: Protocol Specific Exceptions to Expedited Reporting**

For this protocol only, the following Adverse Events/Grades are expected to occur within this population and do not require Expedited Reporting. These events must still be reported via Routine Reporting (see Section 10.6). *

*Report any clinically important increase in the rate of a serious suspected adverse reaction (at your study site) over that which is listed in the protocol or investigator brochure as an expedited event.

*Report an expected event that is greater in severity or specificity than expected as an expedited event.

System Organ Class (SOC)	Adverse event/ Symptoms	CTCAE Grade at which the event will not be expeditedly reported. ¹
General disorders and administration site conditions	Fatigue	≤Grade 3
	Malaise	≤Grade 3
	Cutaneous irritation from imiquimod	≤Grade 3

¹These exceptions only apply if the adverse event does not result in hospitalization. If the adverse event results in hospitalization, then the standard expedited adverse events reporting requirements must be followed.

Specific protocol exceptions to expedited reporting should be reported expeditiously by investigators **ONLY** if they exceed the expected grade of the event.

The following hospitalizations are not considered to be SAEs because there is no “adverse event” (*i.e.*, there is no untoward medical occurrence) associated with the hospitalization:

- Hospitalizations for respite care
- Planned hospitalizations required by the protocol
- Hospitalization planned before informed consent (where the condition requiring the hospitalization has not changed post study drug administration)
- Hospitalization for elective procedures unrelated to the current disease and/or treatment on this trial
- Hospitalization for administration of study drug or insertion of access for administration of study drug
- Hospitalization for routine maintenance of a device (*e.g.*, battery replacement) that was in place before study entry
- Hospitalization, or other serious outcomes for signs and symptoms of progression of the cancer.]

10.4 Expedited Reporting Requirements for IND/IDE Agents

10.41 Phase 1 and Early Phase 2 Studies: Expedited Reporting Requirements for Adverse Events that Occur on Studies under an IND/IDE within 30 Days of the Last Administration of the Investigational Agent/Intervention ^{1, 2}

FDA REPORTING REQUIREMENTS FOR SERIOUS ADVERSE EVENTS (21 CFR Part 312) NOTE: Investigators MUST immediately report to the sponsor ANY Serious Adverse Events, whether or not they are considered related to the investigational agent(s)/intervention (21 CFR 312.64) An adverse event is considered serious if it results in ANY of the following outcomes: 
 1) Death 2) A life-threatening adverse event 3) An adverse event that results in inpatient hospitalization or prolongation of existing hospitalization for ≥ 24 hours 4) A persistent or significant incapacity or substantial disruption of the ability to conduct normal life functions 5) A congenital anomaly/birth defect. 6) Important Medical Events (IME) that may not result in death, be life threatening, or require hospitalization may be considered serious when, based upon medical judgment, they may jeopardize the patient or subject and may require medical or surgical intervention to prevent one of the outcomes listed in this definition. (FDA, 21 CFR 312.32; ICH E2A and ICH E6). 		
ALL SERIOUS adverse events that meet the above criteria MUST be immediately reported to the sponsor within the timeframes detailed in the table below.		
Hospitalization	Grade 1 and Grade 2 Timeframes	Grade 3-5 Timeframes
Resulting in Hospitalization ≥24 hrs	7 Calendar Days	24-Hour 3 Calendar Days
Not resulting in Hospitalization ≥24 hrs	Not required	

Expedited AE reporting timelines are defined as:

- "24-Hour; 3 Calendar Days" - The AE must initially be reported within 24 hours of learning of the AE, followed by a complete expedited report within 3 calendar days of the initial 24-hour report.
- "7 Calendar Days" - A complete expedited report on the AE must be submitted within 7 calendar days of learning of the AE.

¹Serious adverse events that occur more than 30 days after the last administration of investigational agent/intervention and have an attribution of possible, probable, or definite require reporting as follows:

Expedited 24-hour notification followed by complete report within 3 calendar days for:

- All Grade 3, 4, and Grade 5 AEs

Expedited 7 calendar day reports for:

- Grade 2 AEs resulting in hospitalization or prolongation of hospitalization

² For studies using PET or SPECT IND agents, the AE reporting period is limited to 10 radioactive half-lives, rounded UP to the nearest whole day, after the agent/intervention was last administered. Footnote "1" above applies after this reporting period.

Effective Date: May 5, 2011

NOTE: Refer to Section 10.32 for exceptions to Expedited Reporting

10.42 General reporting instructions

Use Mayo Expedited Event Report form

for investigational agents or commercial/investigational agents on the same arm.

Submit to:

For commercial agents:

Submit form

10.43 Reporting of re-occurring SAEs

ALL SERIOUS adverse events that meet the criteria outlined in table 10.41 MUST be immediately reported to the sponsor within the timeframes detailed in the corresponding table. This reporting includes, but is not limited to SAEs that re-occur again after resolution.

10.5 Other Required Reporting

10.51 Unanticipated Problems Involving Risks to Subjects or Others (UPIRTSOS)

Unanticipated Problems Involving Risks to Subjects or Others (UPIRTSOS) in general, include any incident, experience, or outcome that meets **all** of the following criteria:

1. Unexpected (in terms of nature, severity, or frequency) given (a) the research procedures that are described in the protocol-related documents, such as the IRB-approved research protocol and informed consent document; and (b) the characteristics of the subject population being studied;
2. Related or possibly related to participation in the research (in this guidance document, possibly related means there is a reasonable possibility that the

incident, experience, or outcome may have been caused by the procedures involved in the research); and

3. Suggests that the research places subjects or others at a greater risk of harm (including physical, psychological, economic, or social harm) than was previously known or recognized.

Some unanticipated problems involve social or economic harm instead of the physical or psychological harm associated with adverse events. In other cases, unanticipated problems place subjects or others at increased *risk* of harm, but no harm occurs.

Note: If there is no language in the protocol indicating that pregnancy is not considered an adverse experience for this trial, and if the consent form does not indicate that subjects should not get pregnant/impregnate others, then any pregnancy in a subject/patient or a male patient's partner (spontaneously reported) which occurs during the study or within 120 days of completing the study should be reported as a UPIRTSO.

Mayo Clinic Cancer Center (MCCC) Institutions:

If the event meets the criteria for IRB submission as a Reportable Event/UPIRTSO, provide the Reportable Event coversheet and appropriate documentation to [REDACTED] The Mayo Regulatory Affairs Office will review and process the submission to the Mayo Clinic IRB.

10.52 Death

Note: A death on study requires both routine and expedited reporting regardless of causality, unless as noted below. Attribution to treatment or other cause must be provided.

Any death occurring within 30 days of the last dose, regardless of attribution to an agent/intervention under an IND/IDE requires expedited reporting within 24-hours.

Any death occurring greater than 30 days with an attribution of possible, probable, or definite to an agent/intervention under an IND/IDE requires expedited reporting within 24-hours.

Reportable categories of Death

- Death attributable to a CTCAE term.
- Death Neonatal: A disorder characterized by cessation of life during the first 28 days of life.
- Death NOS: A cessation of life that cannot be attributed to a CTCAE term associated with Grade 5.
- Sudden death NOS: A sudden (defined as instant or within one hour of the onset of symptoms) or an unobserved cessation of life that cannot be attributed to a CTCAE term associated with Grade 5.
- Death due to progressive disease should be reported as **Grade 5**
“Neoplasms benign, malignant and unspecified (including cysts and

polyps) – Other (Progressive Disease)” under the system organ class (SOC) of the same name. Evidence that the death was a manifestation of underlying disease (e.g., radiological changes suggesting tumor growth or progression: clinical deterioration associated with a disease process) should be submitted.

10.53 Secondary Malignancy

- A **secondary malignancy** is a cancer caused by treatment for a previous malignancy (e.g., treatment with investigational agent/intervention, radiation or chemotherapy). A secondary malignancy is not considered a metastasis of the initial neoplasm.
- All secondary malignancies that occur following treatment with an agent under an IND/IDE will be reported. Three options are available to describe the event:
 - Leukemia secondary to oncology chemotherapy (e.g., Acute Myelocytic Leukemia [AML])
 - Myelodysplastic syndrome (MDS)
 - Treatment-related secondary malignancy
- Any malignancy possibly related to cancer treatment (including AML/MDS) should also be reported via the routine reporting mechanisms outlined in each protocol.

10.54 Second Malignancy

A second malignancy is one unrelated to the treatment of a prior malignancy (and is NOT a metastasis from the initial malignancy). Second malignancies require ONLY routine reporting unless otherwise specified.

10.55 Pregnancy, Fetal Death, and Death Neonatal

If a female subject (or female partner of a male subject) taking investigational product becomes pregnant, the subject taking should notify the Investigator, and the pregnant female should be advised to call her healthcare provider immediately. The patient should have appropriate follow-up as deemed necessary by her physician. If the baby is born with a birth defect or anomaly, a second expedited report is required.

Prior to obtaining private information about a pregnant woman and her infant, the investigator must obtain consent from the pregnant woman and the newborn infant's parent or legal guardian before any data collection can occur. A consent form will need to be submitted to the IRB for these subjects if a pregnancy occurs. If informed consent is not obtained, no information may be collected.

In cases of fetal death, miscarriage or abortion, the mother is the patient. In cases where the child/fetus experiences a serious adverse event other than fetal death, the child/fetus is the patient.

NOTE: When submitting Mayo Expedited Adverse Event Report reports for “Pregnancy”, “Pregnancy loss”, or “Neonatal loss”, the potential risk of exposure of the fetus to the investigational agent(s) or chemotherapy agent(s) should be documented in the “Description of Event” section. Include any available medical documentation. Include this form:

10.541 Pregnancy

Pregnancy should be reported in an expedited manner as **Grade 3 “Pregnancy, puerperium and perinatal conditions - Other (pregnancy)”** under the Pregnancy, puerperium and perinatal conditions SOC. Pregnancy should be followed until the outcome is known.

10.542 Fetal Death

Fetal death is defined in CTCAE as “A disorder characterized by death in utero; failure of the product of conception to show evidence of respiration, heartbeat, or definite movement of a voluntary muscle after expulsion from the uterus, without possibility of resuscitation.”

Any fetal death should be reported expeditiously, as **Grade 4 “Pregnancy, puerperium and perinatal conditions - Other (pregnancy loss)”** under the Pregnancy, puerperium and perinatal conditions SOC.

10.543 Death Neonatal

Neonatal death, defined in CTCAE as “A disorder characterized by cessation of life occurring during the first 28 days of life” that is felt by the investigator to be at least possibly due to the investigational agent/intervention, should be reported expeditiously.

A neonatal death should be reported expeditiously as **Grade 4 “General disorders and administration - Other (neonatal loss)”** under the General disorders and administration SOC.

10.6 Required Routine Reporting

10.61 Baseline and Adverse Events Evaluations

Pretreatment symptoms/conditions to be graded at baseline and adverse events to be graded at each evaluation per CTCAE v4.0 grading **unless** otherwise stated in the table below:

System Organ Class (SOC)	Adverse event/Symptoms	Baseline	Each evaluation
Blood and lymphatic system disorders	Anemia	X	X
	Febrile Neutropenia		X
Cardiac Disorders	Myocardial infarction		X
Gastrointestinal disorders	Nausea	X	X
	Vomiting	X	X
	Abdominal pain	X	X
	Baseline # of stools	X	

	Diarrhea		X
General disorders and administration site conditions	Fatigue	X	X
	Fever		X
Immune system disorders	Allergic reaction		X
	Anaphylaxis		X
Investigations	Neutrophil count decreased		X
	Platelet count decreased		X
	White blood cell decreased		X
	Aspartate aminotransferase increased	X	X
	Alkaline phosphatase increased	X	X
	Blood bilirubin increased	X	X
Musculoskeletal and connective tissue disorders	Arthralgia	X	X
	Myalgia	X	X
Nervous system disorders	Peripheral sensory neuropathy	X	X

10.62 Submit via appropriate MCCC Case Report Forms (i.e., paper or electronic, as applicable) the following AEs experienced by a patient and not specified in Section 10.6:

10.621 Grade 2 AEs deemed *possibly, probably, or definitely* related to the study treatment or procedure.

10.622 Grade 3 and 4 AEs regardless of attribution to the study treatment or procedure.

10.623 Grade 5 AEs (Deaths)

10.6231 Any death within 30 days of the patient's last study treatment or procedure regardless of attribution to the study treatment or procedure.

10.6232 Any death more than 30 days after the patient's last study treatment or procedure that is felt to be at least possibly treatment related must also be submitted as a Grade 5 AE, with a CTCAE type and attribution assigned.

10.7 Late Occurring Adverse Events

Refer to the instructions in the Forms Packet (or electronic data entry screens, as applicable) regarding the submission of late occurring AEs following completion of the Active Monitoring Phase (i.e., compliance with Test Schedule in Section 4.0).

11.0 Treatment Evaluation Using RECIST 1.1 Guideline

11.1 The first scan after treatment initiation will be performed after the completion of cycle 4 (approximately week 12) and will be then performed every 12 weeks until disease progression is confirmed

Disease progression for this protocol is defined as meeting the RECIST criteria for disease progression on two consecutive evaluations at least 6 weeks apart (see Section 13.2).

11.2 Definitions of Measurable and Non-Measurable Disease

11.21 Measurable Disease

11.211 A non-nodal lesion is considered measurable if its longest diameter can be accurately measured as ≥ 2.0 cm with chest x-ray, or as ≥ 1.0 cm with CT scan, CT component of a PET/CT, or MRI.

11.212 A malignant lymph node is considered measurable if its short axis is ≥ 1.5 cm when assessed by CT scan (CT scan slice thickness recommended to be no greater than 5 mm).

NOTE: *Tumor lesions in a previously irradiated area are not considered measurable disease.*

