2.0 Goals

2.1 Primary

To gain preliminary data of the anti-tumor activity and safety profile of the combination of imiquimod and pembrolizumab in patients with unresectable cutaneous melanoma.

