3.0 Patient Eligibility

3.1 Registration – Inclusion Criteria

- 3.11 Age \geq 18 years.
- 3.12 Histological confirmation of Stage IIIB, IIIC, IVM1a, IVM1b, or IVM1c that is not suitable for surgical resection.
- 3.13 Patients must not have received prior pembrolizumab or other anti-PD1/PDL1 therapies for their metastatic disease.

- 3.14 At least one cutaneous lesion that is amenable to treatment with topical imiquimod.
- 3.15 Measurable disease by RECIST as defined in Section 11.0.
- 3.16 ECOG Performance Status (PS) of 0 or 1 (Appendix I).
- 3.17 The following laboratory values obtained ≤ 14 days prior to registration.
- Absolute neutrophil count (ANC) $\geq 1500/\text{mm}^3$
 - Platelet count $\geq 100,000/\text{mm}^3$
 - Hemoglobin $> 9.0 \text{ g/dL}$ or $\geq 5.6 \text{ mmol/L}$ without transfusion or EPO dependency (within 7 days of assessment).
 - Serum total bilirubin $\leq 1.5 \times \text{ULN}$ or Direct bilirubin $\leq (\text{ULN})$ for subjects with total bilirubin levels $> 1.5 \text{ ULN}$
 - Aspartate transaminase (AST) $\leq 2.5 \times \text{ULN}$ or $\leq 5 \times \text{ULN}$ for subjects with liver metastases.
 - Albumin $\geq 2.5 \text{ mg/dL}$
 - Creatinine $\leq 1.5 \times$ upper limit of normal (ULN)
- NOTE:** Measured or calculated (per institutional standard) creatinine clearance is acceptable $\geq 60 \text{ mL/min}$ for subject with creatinine levels $> 1.5 \times$ institutional ULN. Calculated creatinine clearance can be used in place of creatinine or CrCl and must be $\geq 45 \text{ mL/min}$ using the Cockcroft-Gault formula below:

Cockcroft-Gault Equation:

$$\text{Creatinine clearance for males} = \frac{(140 - \text{age})(\text{weight in kg})}{(72)(\text{serum creatinine in mg/dL})}$$

$$\text{Creatinine clearance for females} = \frac{(140 - \text{age})(\text{weight in kg})(0.85)}{(72)(\text{serum creatinine in mg/dL})}$$

- 3.18 Negative urine or serum pregnancy test done ≤ 72 hours prior to first treatment, for women of childbearing potential only.

If the urine test is positive or cannot be confirmed as negative, a serum pregnancy test will be required.

- 3.19a Provide informed written consent.
- 3.19b Willing to return to enrolling institution for follow-up.
- 3.19c Willing to provide tissue from a newly obtained core or excisional biopsy of a tumor lesion in appropriate low risk cutaneous lesions.

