4.0 Test Schedule

Tests and Procedures	≤28 Days prior to Registration	Day 1 (+/-3 days) of each cycle	End of Treatment	Observation	
				Every 12 (+/- 2) weeks for months 24 thru 36 post registration	at progression
History and Physical Examination, wt, PS	X	X	X	X	X
Height	X				
Adverse Events Assessment	X	X	X	X	X
Pregnancy Test – Urine or Serum –HCG ¹		X ⁶			
CBC w/diff	X ²	X	X	X	X
Renal Profile: Sodium, Potassium, Chloride, Bicarbonate, Creatinine, Bun, Glucose	X ²	X	X	X	X
Albumin, bilirubin total and direct, alkaline phosphatase, total protein, AST, and ALT	X ²	X			
FT4 and TSH	X	X	X		
Disease Evaluation ³	X	X ⁴	X	X	X
Research Tissue Collection ^R		X ⁵			
Photograph of lesions	X	X	X	X	X

1. For women of childbearing potential only. Must be done ≤72 hours prior to registration.

2. ≤14 Days prior to Registration

3. Radiographic tumor imaging assessments must include CT scan, PET/CT, or MRI of the chest, abdomen, and pelvis. CT scan or MRI of the brain with contrast will only be performed if symptoms or signs of CNS metastasis are present. Use same imaging throughout the study.

4. At the completion of cycle 4 (approximately week 12) and then at completion of every 4th cycle (approximately every 12 weeks) thereafter (±7days) until PD.

5. Tissue specimens must be collected and submitted after registration but prior to the start of treatment, at completion of cycles 2 and 4 (approximately weeks 6 and 12).

6. For women of childbearing potential only. Must be done ≤ 72 hours prior to start of treatment. Must be repeated if pre-registration test is > 72 hours prior to the start of treatment.

R Research funded (see Section 19.0)

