11.22 Non-Measurable Disease

All other lesions (or sites of disease) are considered non-measurable disease, including pathological nodes (those with a short axis ≥ 1.0 to < 1.5 cm). Bone lesions, leptomeningeal disease, ascites, pleural/pericardial effusions, lymphangitis cutis/pulmonis, inflammatory breast disease, and abdominal masses (not followed by CT or MRI), are considered as non-measurable as well.

NOTE: ‘Cystic lesions’ thought to represent cystic metastases can be considered as measurable lesions, if they meet the definition of measurability described above. However, if non-cystic lesions are present in the same patient, these are preferred for selection as target lesions.

Lymph nodes that have a short axis < 1.0 cm are considered non- pathological (i.e., normal) and should not be recorded or followed.

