11.43 Response Criteria

11.431 All target lesions and target lymph nodes followed by CT/MRI/PET-CT/Chest X-ray/physical examination must be measured on re-evaluation at evaluation times specified in Section 11.1. Specifically, a change in objective status to either a PR or CR cannot be done without re-measuring target lesions and target lymph nodes.

Note: Non-target lesions and non-target lymph nodes should be evaluated at each assessment, especially in the case of first response or confirmation of response. In selected circumstances, certain non-target organs may be evaluated less frequently. For example, bone scans may need to be repeated only when complete response is identified in target disease or when progression in bone is suspected.

11.432 Evaluation of Target Lesions

- Complete Response (CR): All of the following must be true:
 - a. Disappearance of all target lesions.
 - b. Each target lymph node must have reduction in short axis to <1.0 cm.
- Partial Response (PR): At least a 30% decrease in PBSD (sum of the longest diameter for all target lesions plus the sum of the short axis of all the target lymph nodes at current evaluation) taking as reference the BSD (*see* Section 11.41).
- Progression (PD): At least one of the following must be true:
 - a. At least one new malignant lesion, which also includes any lymph node that was normal at baseline (< 1.0 cm short axis) and increased to ≥ 1.0 cm short axis during follow-up.

- b. At least a 20% increase in PBSD (sum of the longest diameter for all target lesions plus the sum of the short axis of all the target lymph nodes at current evaluation) taking as reference the MSD (Section 11.41). In addition, the PBSD must also demonstrate an absolute increase of at least 0.5 cm from the MSD.
- c. See Section 11.32 for details in regards to the requirements for PD via FDG-PET imaging.

- Stable Disease (SD): Neither sufficient shrinkage to qualify for PR, nor sufficient increase to qualify for PD taking as reference the MSD.

11.433 Evaluation of Non-Target Lesions & Non-target Lymph Nodes

- Complete Response (CR): All of the following must be true:
 - a. Disappearance of all non-target lesions.
 - b. Each non-target lymph node must have a reduction in short axis to <1.0 cm.
- Non-CR/Non-PD: Persistence of one or more non-target lesions or non-target lymph nodes.
- Progression (PD): At least one of the following must be true:

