16.0 Statistical Considerations and Methodology

16.1 This pilot study will enroll 10 patients to gain preliminary data on the anti-tumor activity and safety profile of the combination of imiquimod and pembrolizumab in patients with unresectable cutaneous melanoma.

If there are no tumor responses documented among these 10 patients, then upper bound of a one-sided 95% confidence interval for the tumor response rate would be 25.9%.

All patients meeting the eligibility criteria who have signed a consent form and have begun treatment will be evaluable for assessment of all of the clinical endpoints.

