16.2 Tumor response rate and duration of response

- 16.21 Tumor response rate is defined as percentage of patients whose objective disease status meets the criteria for RECIST criteria for partial or complete response on two consecutive disease evaluations at least 12 weeks apart.
- 16.22 For those patients who disease had a partial or complete response to treatment on two consecutive disease evaluations at least 12 weeks apart, the duration of treatment response is defined as the time from registration to disease progression.

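### A skin lesion that does not reach 1.0 cm on CT or MRI is non-target, so its shrinkage cannot by itself produce a partial response; Section 11.431 conflicts with this

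*Combined protocol and SAP*

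**What the plan says.** The primary goal (2.1) is "To gain preliminary data of the anti-tumor activity and safety profile of the combination of imiquimod and pembrolizumab" in unresectable cutaneous melanoma. Section 16.21 defines the anti-tumor endpoint: "Tumor response rate is defined as percentage of patients whose objective disease status meets the criteria for RECIST criteria for partial or complete response", confirmed on a second consecutive evaluation. Section 16.1 sets the size: "This pilot study will enroll 10 patients".

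Eligibility asks for at least one skin lesion that can be treated with imiquimod (3.14), with no size requirement. Separately, it asks for "Measurable disease by RECIST as defined in Section 11.0" (3.15).

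On measurability, 11.211 reads "A non-nodal lesion is considered measurable if its longest diameter can be accurately measured as" at least 2.0 cm on chest x-ray, or at least 1.0 cm on CT, the CT component of a PET/CT, or MRI. Section 11.22 adds: "All other lesions (or sites of disease) are considered non-measurable disease". Target lesions are drawn from those measurable under 11.21 (11.41), and non-measurable sites are non-target (11.42).

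Section 11.431, however, says: "All target lesions and target lymph nodes followed by CT/MRI/PET-CT/Chest X-ray/physical examination must be measured on re-evaluation".

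Footnote 3 to the test schedule in 4.0 says: "Radiographic tumor imaging assessments must include CT scan, PET/CT, or MRI of the chest, abdomen, and pelvis". Brain imaging is done only for symptoms or signs. Lesion photographs are scheduled at baseline and at every cycle, but no response rule uses them.

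**The concern.** The trial adds a cream applied to skin lesions to a systemic drug, yet the definition that feeds the response endpoint gives those lesions no route to target status except CT or MRI. If a treated lesion falls outside that route, the endpoint does not register its partial shrinkage, and its complete disappearance does not turn stable disease into a response. Its growth still counts against the patient.

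Two further consequences follow. A patient whose only disease is skin lesions that CT/MRI cannot measure is ineligible, although 3.12 admits stage IIIB and IIIC disease. And because 11.431 mentions physical examination while 11.21 does not, two careful assessors could score the same patient differently.

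**Working it through.** **1. The plan's own figure.** For 0 responses in 10, the exact one-sided 95% upper bound is 1 - 0.05^(1/10) = 0.2589. This matches the 25.9% in 16.1. The measurability rule does not affect it; it affects which patients can be counted as responders.

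**2. Routes to target status for a skin lesion.**
- Chest x-ray: 11.32 accepts only lesions surrounded by aerated lung, so this route is closed to skin.
- CT, CT part of PET/CT, or MRI: open if the lesion measures at least 1.0 cm and lies in a scanned field. The required field is chest, abdomen and pelvis, so limb and scalp lesions are on no required scan.
- Physical examination: named in 11.431, but 11.21 gives no size criterion for it, 11.32 does not list it, and 11.41 ties target lesions to 11.21.

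**3. What a non-target lesion can do (11.432, 11.433, 11.44).**
- PR requires at least a 30% fall in the target sum. Non-target lesions are not in that sum.
- Target SD with non-target CR, or with Non-CR/Non-PD, is SD overall.
- Target CR with a persisting non-target lesion is PR, so persistence blocks CR.
- Unequivocal non-target progression is PD, whatever the targets show.

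**4. When counting the skin lesion would change the result.** Let v be the sum of the stable scan-measured targets and s the skin lesion's baseline diameter. If the skin lesion disappears, the change in the combined sum is -s/(v + s). PR needs s/(v + s) >= 0.30, so s >= (0.3/0.7)v = 0.429v. For v = 3.0 cm this is s >= 1.29 cm. All sizes below are assumed; the documents give none.

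| Stable scan targets (cm) | Skin lesion (cm) | Change if skin is a target | As written |
|---|---|---|---|
| 3.0 | 1.5 to 0 | -1.5/4.5 = -33.3%, PR | 0%, SD |
| 3.0 | 1.0 to 0 | -1.0/4.0 = -25.0%, SD | 0%, SD |
| 3.0 + 3.0 | 1.0 to 0 | -1.0/7.0 = -14.3%, SD | 0%, SD |
| 2.0 | 2.0 to 0.6 (70% shrinkage) | -1.4/4.0 = -35.0%, PR | 0%, SD |

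A PR must also be confirmed at a second evaluation (16.21).

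**5. Effect on the rate.** One reclassified patient is 1/10 = 10 percentage points. Going from 0 to 1 responder moves the upper limit of an exact 90% interval from 25.9% to 39.4%. For comparison, 1.9c11 expects about 25% (after ipilimumab) and 40% (front line) with pembrolizumab alone.

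**The case against.** Several stronger readings are tempting, and the documents do not support them.

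- **That the endpoint is blind to skin lesions in general.** A skin lesion of at least 1.0 cm on CT/MRI can be a target, and footnote 3 sets a minimum imaging field rather than a limit. With no data on lesion size or site, the share affected cannot be stated.
- **That every patient whose treated lesions clear is a lost responder.** Step 4 shows that this depends on the skin lesion's share of the target sum, and on confirmation. A stable skin target would also dilute visceral shrinkage, so the change could move a patient either way.
- **That clearing the treated lesions is a non-target CR.** Section 7.4 leaves at least one lesion untreated when there is more than one. If that lesion is non-target and persists, the status is Non-CR/Non-PD.
- **That the ruler-or-calipers line in 11.31 is a second contradiction.** It is a general rule for recording measurements. Only 11.431 conflicts with 11.21.

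It is also fair to say that this is a descriptive pilot without a hypothesis test. Section 1.64 gives distant failure as the reason for adding systemic therapy, so whole-body response is a relevant outcome. A single-arm response rate would not separate imiquimod from pembrolizumab even with skin lesions counted. Finally, caliper margins can be obscured by the local reactions listed in 15.22 and by the biopsies at 6 and 12 weeks. These arguments limit the size of the point and shape the remedy. They do not give skin lesions a measurability rule or reconcile 11.21 with 11.431.

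**Conclusion.** The point stands in limited form. As written, a skin lesion that does not measure at least 1.0 cm on CT/MRI is non-target. Its shrinkage or disappearance cannot by itself produce a PR, although its progression can cause PD and its persistence blocks CR. A patient with only such lesions fails 3.15. Section 11.431 is inconsistent with this.

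The effect is 10 percentage points per patient actually reclassified. How many patients that would be is unknown. Reclassification from SD to PR requires the combined target sum to fall by at least 30%, with confirmation. The conclusion rests on taking 11.41 literally, so that the mention of physical examination in 11.431 does not itself create target lesions. If the sponsor intended otherwise, the missing size criterion still has to be supplied.

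**What to change.** Reconcile 11.21 with 11.431 by adding that a cutaneous lesion with longest diameter of at least 1.0 cm by caliper, photographed with a ruler, is measurable and may be a target lesion. The matching changes are:

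- 11.32: add caliper measurement of skin lesions to the acceptable modalities.
- 11.31: exempt caliper-measured skin lesions from the sentence requiring CT for patients with only lesions of 1 to under 2 cm; otherwise the new rule collides with it.
- 4.0: list caliper measurement under Disease Evaluation, at baseline and the response evaluation times.
- 18.5: accept the measurement record and photograph as documentation of response, alongside the imaging report.
- 11.41: state that a lesion excised for biopsy (3.19c permits excision) is not a target lesion, so that its removal is not counted as shrinkage.
- 16.2: also report the response rate on scan-measured lesions alone, as a sensitivity analysis.

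Because 3.15 points to Section 11, the new criterion would also widen eligibility; the sponsor should confirm that this is wanted. If the sponsor prefers scan-measured disease only, the minimum is to say so and remove physical examination from 11.431.

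The cost is a short amendment and a few minutes at visits where lesions are already examined and photographed. The sample size and the 25.9% bound do not change. The real downside is noisier measurement: caliper readings vary more than CT, and imiquimod reactions and core biopsies can blur the lesion margin. The sensitivity analysis is there to show how far the result depends on those readings.
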